## INSTRUCTIONS:

- Use “SOCIAL TEMPLATE PROTOCOL (HRP-580)” to prepare a document with the information from following sections.
- If your research involves physical or invasive interventions, e.g., physical examinations, blood draws or specimen collection, or exercise activities, then you must use “MEDICAL TEMPLATE PROTOCOL (HRP-590)” instead.
- If your research involves a drug or device, then you must use “MEDICAL TEMPLATE PROTOCOL (HRP-590) instead. If you are unsure about whether your study involves a drug or device, please contact the IRB office at [[contact]](mailto:[contact]) to obtain guidance as you prepare your protocol.
- Depending on the nature of what you are doing, some sections may not be applicable to your research. If so mark as “NA”. For example, research involving a retrospective chart review may have many sections with N/A. For subsections, like 1.x or 8.x, you can delete it if it’s not applicable.
- After you submit your protocol for review in ETHOS, your protocol will be saved there. You should use that saved version as your starting point for edits to the next version. You may choose to track protocol versions for yourself outside of ETHOS; however, you should ensure that any version you edit is the same as the most recently approved version in ETHOS.
- As you are writing the protocol, remove all instructions in italics so that they are not contained in the final version of your protocol.
- See the Table of Contents instructions for updating page numbers after you complete your protocol.

## REVISION HISTORY

Revision #	Version Date	Summary of Changes	Consent Change?

## ABBREVIATIONS/DEFINITIONS

*Include any abbreviations or definitions for key or technical terms you use in your protocol.*

- AIDS Acquired Immunodeficiency Syndrome
- ART Antiretroviral Therapy
- AUDIT Alcohol Use Disorders Identification Test
- BSSS-4 Brief Sensation Seeking Scale
- CASI Computer Assisted Self-Interview
- CES-D Center for Epidemiologic Studies Depression Scale
- CFR Code of Federal Regulations
- CHEST Center for HIV Educational Studies & Training
- HIPAA Health Insurance Portability and Accountability Act
- HIV Human Immunodeficiency Virus
- IMB Information-Motivation-Behavioral Skills
- IMB-AAQ IMB ART Adherence Questionnaire
- IRB Institutional Review Board
- MASRI Medication Adherence Self-report Inventory
- MSM Men who have Sex with Men
- NICHD National Institute of Child Health and Development
- NIDA National Institute on Drug Abuse
- NIH National Institutes of Health
- NYC New York City
- PI Principal Investigator
- PLWH People Living With HIV
- OHRP Office for Human Research Protections
- RCG Radiant Creative Group
- RCT Randomized Controlled Trial
- SMS Short Message Service
- SSL Secure Sockets Layer
- TWM Thrive With Me
- UMN University of Minnesota
- VL Viral Load
- YO Years Old

PROTOCOL TITLE: A Technology-Delivered Peer-to-Peer Support ART Adherence

Intervention for Substance-using HIV+ Adults

VERSION DATE: 4/2/18

## STUDY SUMMARY

Study Title	A Technology-Delivered Peer-to-Peer Support ART Adherence Intervention for Substance-using HIV+ Adults
Study Design	Randomized Controlled Trial
Primary Objective	Primary aims (Aims 1 and 2) are to examine the efficacy of the online and mobile-enabled TWM intervention in a full-scale randomized controlled trial.
Secondary Objective(s)	Aim 3 (a secondary aim) is to examine the effects of the intervention on theory-based change processes (i.e., IMB factors and social support) for improving VL, ART adherence, and substance use outcomes.
Primary Study Intervention or Interaction	The “Thrive with Me” (TWM) intervention is a technology-delivered peer-to-peer social support intervention grounded in the Information, Motivation, and Behavioral Skills (IMB) model for HIV-positive men who have sex with men (MSM). In addition to asynchronous peer-to-peer support capabilities, the TWM intervention provides participants with Antiretroviral Therapy (ART) adherence self-monitoring tools, medication dose reminders, and HIV-related informational content.
Study Population	HIV-positive men who have sex with men
Sample Size (number of participants)	400
Study Duration for Individual Participants	12 months

## 1.0 Objectives

### 1.1 Purpose:

The “Thrive with Me” (TWM) intervention is a technology-delivered peer-to-peer social support intervention grounded in the Information, Motivation, and Behavioral Skills (IMB) model for HIV-positive men who have sex with men (MSM). In addition to asynchronous peer-to-peer support capabilities, the TWM intervention provides participants with Antiretroviral Therapy (ART) adherence self-monitoring tools, medication dose reminders, and HIV-related informational content. The study will be based on the encouraging findings of the TWM pilot study (completed in 2011) and the need for novel, evidence-based effective ART adherence interventions.

## 2.0 Background

### 2.1 Significance of Research Question/Purpose:

Fifty thousand persons are estimated to be infected with HIV in the US each year [1]. In 2011, men who have sex with men (MSM) accounted for 65% of all new infections and were the only transmission group for which HIV infections did not show a year-over-year decline [1]. Current US Guidelines for the Use of Antiretroviral Agents [2] state that undetectable viral load (VL) “is the most important indicator of initial and sustained response to ART” (p. C-5), which requires that people living with HIV (PLWH) demonstrate sufficient and sustained adherence to antiretroviral therapy (ART). Optimal ART adherence reduces excess morbidity and mortality among PLWH [3] and lowers the probability of forward transmission to sexual partners [4]. However, it is estimated that only between 19-25% of all PLWH and 27% of MSM with HIV are virally suppressed [5, 6]. Despite the disproportionate burden of HIV in MSM communities, only 2 of 10 medication adherence interventions included in CDC’s Compendium of Evidence-based Behavioral Interventions are tailored to MSM; one is a provider implemented approach evaluated over a decade ago and the other is an intensive one-on-one counseling approach. Clearly, advancing targeted and innovative ART adherence interventions for HIV-positive MSM remains a high priority [7].

Technology-based ART adherence approaches have proliferated in recent years [8, 9] due to the widespread adoption of technology across sociodemographic groups [10], their ability to reach a broad audience, and their low implementation costs [11]. However, recent computerized ART adherence interventions [12, 13] are individually delivered and fail to leverage peer-to-peer interactivity that has come to symbolize Web 2.0 [14]. Peer-to-peer support is a recommended strategy to improve ART adherence [7], is widely used by PLWH

PROTOCOL TITLE: A Technology-Delivered Peer-to-Peer Support ART Adherence

Intervention for Substance-using HIV+ Adults

VERSION DATE: 4/2/18

[15], and has enormous immediate appeal as a generalizable intervention approach. Furthermore, peer support interventions provide unique social incentives to maintain high engagement in ART adherence interventions.

## 2.2 Preliminary Data:

To address the lack of generalizable interventions for MSM and leverage innovations in Internet and peer-to-peer social media, our team developed and piloted the “Thrive with Me” (or TWM) technology-delivered and theoretically-grounded peer-to-peer social support intervention [16] to improve ART adherence among HIV-positive MSM. In addition to direct peer-to-peer communication features, participants were given options for self-monitoring ART adherence, receiving ART dose reminders, and viewing relevant online HIV informational content. Among the 123 MSM in the pilot, 90% were retained at 1month follow-up, and participants rated the intervention high in perceived information and system quality, usefulness, and overall satisfaction (Means>5.0 on a 1-7 scale). Men randomized to receive the TWM intervention showed improvement across all ART adherence outcomes compared to control participants, with greatest benefits for current drug-using MSM.

## 2.3 Existing Literature:

*See sections 2.1 and 26.0.*

# 3.0 Study Endpoints/Events/Outcomes

## 3.1 Primary Endpoint/Event/Outcome:

**Primary Aim 1:** Determine the efficacy of the *TWM* intervention to increase the proportion of virally suppressed HIV-positive MSM at post-intervention time points.

**H1:** A higher proportion of participants in the TWM intervention than control participants will have undetectable VL at post-intervention time points.

**Primary Aim 2:** Assess whether the *TWM* intervention is most beneficial for HIV-positive MSM who report recent drug use at baseline compared to HIV-positive MSM who do not.

**H2:** Recent drug-using participants in the TWM intervention will demonstrate greatest improvements in VL and self-reported ART adherence at post-intervention time points compared to non-drug-using participants.

## 3.2 Secondary Endpoint(s)/Event(s)/Outcome(s):

**Secondary Aim 3:** Examine the effects of the *TWM* intervention on theory-based change process (i.e., IMB factors and social support) for improving VL, ART adherence, and drug use outcomes.

PROTOCOL TITLE: A Technology-Delivered Peer-to-Peer Support ART Adherence

Intervention for Substance-using HIV+ Adults

VERSION DATE: 4/2/18

**H3:** Tailored adherence information, motivation for adherence, adherence behavioral skills, and peer social support will be associated with VL suppression and improved ART adherence and drug use outcomes.

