The primary outcome measure is biological viral load (VL) at each assessment period. Specifically, blood draws will be taken at baseline, immediate post-intervention, 6- and 12-month post-intervention follow-up assessment points to assess the effects of the TWM intervention on VL, the most important biological marker for adherence. Blood will be drawn by a certified phlebotomist at the CHEST in NYC and analyzed by Quest Diagnostics. Plasma VL is considered undetectable at <20 copies/mm^3 and we will provide test results to participants after each visit. Men will take urine screens at each assessment time point to assess for the following illicit substances: cocaine, methamphetamines, marijuana, opiates, and PCP, using the Integrated E-Z Split Key Cup II-5 panel (Innovacon Laboratories). This test is capable of detecting drugs from one to four days after use, except for chronic marijuana use, which can be detected for up to

PROTOCOL TITLE: A Technology-Delivered Peer-to-Peer Support ART Adherence

Intervention for Substance-using HIV+ Adults

VERSION DATE: 4/2/18

30 days. Although the urine toxicology procedures will not permit objective verification of self-report for the entire follow-up interval, it will provide some means of verifying abstinence versus non-abstinence from drugs. Research staff at CHEST have extensive experience in collecting and processing urine samples.

A full list of survey items are attached with this application (Measures). The primary biological measure (VL) will be examined against self-reported ART adherence items (collected via computerized surveys). Items adapted from the Medication Adherence Self-report Inventory (MASRI) (see attached survey items) will be used to assess dimensions of ART adherence in the past 30 days, including the percentage (0-100%) of overall ART correctly taken and the percentage of ART taken within 2 hours of the correct dose time.

Secondary outcome measures will include a) self-reported adherence information, motivation, and behavioral skills by completing the IMB-AAQ which is a 33-items measure that assess adherence-related information and b) a modified version of two social support questionnaires to assess social support.

Other Self-Report Measures: The following self-report measures will also be collected as part of the TWM trial:

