The social support component of the website is a social network page similar to Facebook, but with targeted content being placed in the feed. TWM intervention staff will create approximately 300 "Thrive Tips" based on addressing barriers identified in the IMB-AAQ survey (all participants take the IMB-AAQ at baseline and this survey is included in the attached appendices under Measures) . Participants will see 4 unique Thrive Tips per day posted to their daily feed. If a participant has identified specific barriers to medication adherence (e.g. fear of someone seeing them take their medications), the Thrive Tips associated with their identified barriers will be highlighted differently in their personal feed to draw more attention to them. Participants can comment on the Thrive Tips to start discussions with other members, or they can start their own topics of discussion. Research staff may also pose questions to the group to spur discussion among members. Research staff will monitor the page daily for hostile interactions or misinformation. Hostile interactions can be flagged by users or admins and removed. In the pilot trial of TWM, admins found that other users would often correct misinformation in a prompt manner and research staff rarely had to step in. Our intention is for users to create community throughout these interactions and also to demonstrate leadership in the group by either starting topics, sharing information, and/or correcting misinformation with minimal guidance from research staff. Participants will be able to privately message with research staff through the TWM website. Participants will not be able to privately message each other through the website. All 300 Thrive Tips will be made available over the course of the first 75 days of the intervention. After the first 75 days, the intervention group will take another IMB-AAQ through the TWM website to see if their medication adherence barriers have changed. The 300 Thrive Tips will be re-ordered and released 4 per day for the remaining 75 days of the intervention.

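### Aim 3 asks what TWM does to the IMB factors and social support, but H3 tests only whether those factors are associated with outcomes, and no post-baseline arm comparison of them is planned

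*Protocol*

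**What the plan says.** Section 3.2 states Aim 3 as examining the effects of TWM "on theory-based change process (i.e., IMB factors and social support) for improving VL, ART adherence, and drug use outcomes". The single hypothesis under it, H3, is that tailored information, motivation, "adherence behavioral skills, and peer social support will be associated with VL suppression", and with better adherence and drug use results. H3 mentions neither the control arm nor a mediation path. H1, in section 3.1, shows how the protocol words an arm comparison when it wants one: "A higher proportion of participants in the TWM intervention than control participants will have undetectable VL at post-intervention time points".

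Section 3.3 gives these measures outcome status: "Secondary outcome measures will include a) self-reported adherence information, motivation, and behavioral skills by completing the IMB-AAQ", with social support as item b). It does not say at which visits they are collected. The lists of repeated measures in sections 3.3 and 5.1 name VL and adherence, with intervention use in one and drug use in the other, but not the IMB factors or social support. For the IMB-AAQ, section 4.1 says that "all participants take the IMB-AAQ at baseline" and that later "After the first 75 days, the intervention group will take another IMB-AAQ through the TWM website to see if their medication adherence barriers have changed".

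Section 17.1 fits its Condition-by-Time models to undetectable VL and ART adherence. It adds effect modification by drug use, exploratory baseline subgroups, and an analysis of intervention exposure within the TWM arm. The SAP lists the IMB-AAQ and social support under psychosocial characteristics, uses psychosocial factors as candidate predictors for imputation, compares arms at baseline, and fits its GEE to undetectable VL only.

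**The concern.** The aim is a causal question about TWM that randomisation can answer. The hypothesis is an observational question about men with higher and lower scores. Men with better adherence skills or more support may well be suppressed more often whichever arm they are in, so H3 can be supported when TWM moves none of these scores.

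A supported H3, reported under Aim 3, invites the conclusion that TWM works through its theory, although the test does not involve TWM. Meanwhile the comparison that would answer Aim 3, on measures the protocol already calls secondary outcomes, appears in neither analysis plan.

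**Working it through.** **1. The plan's own figure.** The documents give no power or sample-size figure for Aim 3. The only one, in section 17.2, concerns VL: 60% versus 46% with 200 per arm. The power level and sidedness are not stated. For two proportions, two-sided 0.05, no continuity correction:

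- Mean proportion (0.60 + 0.46)/2 = 0.53; √(2 × 0.53 × 0.47) = 0.706
- √(0.60 × 0.40 + 0.46 × 0.54) = √0.4884 = 0.699
- z = (0.14 × √200 − 1.96 × 0.706)/0.699 = (1.980 − 1.383)/0.699 = 0.85, so power is about 80%

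The figure reproduces at conventional 80% power. It supplies the n used below and has no other bearing on Aim 3.

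**2. Which planned analysis could answer Aim 3?**

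| Planned analysis | Outcome | Arm comparison of IMB or support after baseline? |
|---|---|---|
| H3 (3.2) | VL, adherence, drug use | No; association only |
| Condition-by-Time models (17.1) | VL, adherence | No |
| Drug-use and other subgroup analyses (17.1) | As above | No |
| Exposure analysis (17.1) | Adherence, TWM arm only | No |
| Baseline tests (SAP) | Baseline characteristics | No; baseline only |
| Imputation (SAP) | Missing variables and VL | No; psychosocial factors are predictors |
| GEE (SAP) | Undetectable VL | No |

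**3. How often would H3 be supported if TWM did nothing?** The setup was 200 men per arm, one standardised factor M with the same distribution in both arms, and log-odds of undetectable VL = ln(0.6/0.4) + ln(OR) × M. Undetectability is then about 60%, the baseline level in section 17.2. The OR per SD of M is assumed; the documents give none. The H3 test compares M between undetectable and detectable men in both arms together. The Aim 3 test compares M between arms. Both are t-tests at 0.05, with 4,000 simulated trials per row.

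| Assumed OR per SD | H3 association test positive | Arm comparison positive |
|---|---|---|
| 1.0 | 5.3% | 4.8% |
| 1.2 | 43% | 5.5% |
| 1.35 | 83% | 4.9% |
| 1.5 | 97% | 5.0% |
| 2.0 | 100% | 4.8% |

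The simulation error on a 5% rate is √(0.05 × 0.95/4000) = 0.34 points, so the last column is consistent with 5% throughout.

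**4. Hand check.** With 240 undetectable and 160 detectable men, the groups differ in M by roughly ln(OR) SDs, so the expected z is about ln(OR) × √(240 × 160/400) = 9.80 × ln(OR).

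- OR 1.2: 0.182 × 9.80 = 1.79; 1.79 − 1.96 = −0.17, or 43%
- OR 1.35: 0.300 × 9.80 = 2.94; 2.94 − 1.96 = 0.98, or 84%
- OR 1.5: 0.405 × 9.80 = 3.97; 3.97 − 1.96 = 2.01, or 98%
- OR 2.0: 0.693 × 9.80 = 6.79; 6.79 − 1.96 = 4.83, or about 100%

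These agree with the simulation to within about a point.

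**The case against.** The best defence is that Aim 3 is itself worded as an effect of the intervention, that section 3.3 names the scores as secondary outcomes of a randomised trial, and that the same section says the experimental comparison together with survey data will be used to examine TWM's effects. No sentence says that supporting H3 satisfies Aim 3. The efficacy criterion in section 17.1 rests on adherence and VL, so no efficacy claim depends on H3. All of this stands, and it limits the consequence. It does not supply an analysis: an analyst following H3, section 17.1 and the SAP would never compare the arms on these scores after baseline.

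H3 could also be read as referring to TWM components, tested by the exposure analysis. That analysis stays within the TWM arm and relates usage to adherence, so it is no more randomised and does not show that any process changed.

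The percentages are illustrative. They assume one factor, one outcome and 400 complete cases. H3 names four factors and three outcomes, and requiring every pair to be significant would lower its success rate. The contrast with about 5% remains wherever a real association exists.

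Three stronger readings are tempting and are not supported:

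- **That the IMB-AAQ after day 75, taken by TWM men only, is the flaw.** Section 4.1 describes it as a check on barriers before the Thrive Tips are re-ordered, which makes it a tailoring step. The gap in H3 would remain if both arms took it. Giving it to control men would put adherence content into a condition that section 5.2 deliberately keeps off medication adherence.
- **That control men have no follow-up scores.** Visits are unstated in the text, but section 3.3 points to an attached measures list that is not available here.
- **That men told they are undetectable then rate themselves as more skilled at the same visit.** Sections 3.3 and 5.2 give results after each visit, so the month-5 result cannot shape the month-5 answers.

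**Conclusion.** The point holds as a mismatch between a secondary aim and its hypothesis, with no analysis in either document to bridge it. Aim 3 concerns TWM's effect on the change processes; H3 and the planned models do not estimate that effect. With no TWM effect, the association test would be positive in about 43% to 100% of trials for assumed odds ratios of 1.2 to 2.0 per SD, against about 5% for an arm comparison. The exact rates rest on those assumptions. The logic needs only that some factor is truly associated with an outcome.

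A reader might go further and infer that the trial could claim efficacy through H3, or that Aim 3 cannot be answered from its data. The documents support neither. Efficacy is tied to VL and adherence, and if both arms completed these scales at follow-up, Aim 3 can be answered by analysis alone.

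**What to change.** 1. Reword H3 in section 3.2: *Compared with control, TWM will increase IMB-AAQ information, motivation and behavioral-skills scores and social support at immediate post-intervention.*
2. Add to section 17.1 and the SAP a TWM-versus-control comparison of each score, adjusted for its baseline value, using the follow-up surveys in both arms. State the visits at which the scales are collected.
3. Make the link to outcomes a second step, labelled exploratory: immediate post-intervention scores as mediators of VL and adherence at the later visits. State that the path from mediator to outcome is not protected by randomisation, so this step needs assumptions about confounding that the first does not.

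The cost is a few lines of text and some analysis, with no new procedure, provided the scales were given to both arms at follow-up. If they were not, the SAP should say that Aim 3 cannot be assessed as a randomised comparison. The SAP is dated April 2022 and written in the past tense, so the change should be dated and, if results have already been seen, identified as added afterwards.

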### 3.3. Additional information about study design and endpoints

Primary aims (Aims 1 and 2) are to examine the efficacy of the online and mobile-enabled TWM intervention in a full-scale randomized controlled trial. HIV-positive adults (all men who have sex with men [MSM]) with detectable HIV viral load (VL) residing in New York City will be randomized to receive the TWM intervention or an information-only HIV/ART intervention for a 6-month period. Recruitment will be stratified by recent drug use, such that half will report recent illicit drug use. HIV VL, validated self-reported ART adherence, and intervention utilization measures will be collected at baseline, post-intervention, and 6-, and 12-month follow up. We hypothesize that participants in the TWM intervention will demonstrate significant improvements in self-reported ART adherence and VL at each follow-up time point compared to control participants, with greatest improvements among recent drug users.

We will use an experimental research design to assess the effects of the TWM intervention on HIV VL and self-reported ART adherence among the total sample, drug-using participants, and non-drug-using participants. Data collected from participants will only be used for the purposes of this study. Data will be collected in the form of biologic specimens (blood AND urine) and computerized surveys to assess socio-demographic variables, psychological measures, and behavioral measures (e.g., drug use, ART adherence). Biological specimens and computerized surveys will be collected on-site at the Center for HIV Educational Studies and Training (CHEST) at Hunter College in New York City (NYC).

The primary outcome measure is biological viral load (VL) at each assessment period. Specifically, blood draws will be taken at baseline, immediate post-intervention, 6- and 12-month post-intervention follow-up assessment points to assess the effects of the TWM intervention on VL, the most important biological marker for adherence. Blood will be drawn by a certified phlebotomist at the CHEST in NYC and analyzed by Quest Diagnostics. Plasma VL is considered undetectable at <20 copies/mm^3 and we will provide test results to participants after each visit. Men will take urine screens at each assessment time point to assess for the following illicit substances: cocaine, methamphetamines, marijuana, opiates, and PCP, using the Integrated E-Z Split Key Cup II-5 panel (Innovacon Laboratories). This test is capable of detecting drugs from one to four days after use, except for chronic marijuana use, which can be detected for up to

PROTOCOL TITLE: A Technology-Delivered Peer-to-Peer Support ART Adherence

Intervention for Substance-using HIV+ Adults

VERSION DATE: 4/2/18

30 days. Although the urine toxicology procedures will not permit objective verification of self-report for the entire follow-up interval, it will provide some means of verifying abstinence versus non-abstinence from drugs. Research staff at CHEST have extensive experience in collecting and processing urine samples.

A full list of survey items are attached with this application (Measures). The primary biological measure (VL) will be examined against self-reported ART adherence items (collected via computerized surveys). Items adapted from the Medication Adherence Self-report Inventory (MASRI) (see attached survey items) will be used to assess dimensions of ART adherence in the past 30 days, including the percentage (0-100%) of overall ART correctly taken and the percentage of ART taken within 2 hours of the correct dose time.

Secondary outcome measures will include a) self-reported adherence information, motivation, and behavioral skills by completing the IMB-AAQ which is a 33-items measure that assess adherence-related information and b) a modified version of two social support questionnaires to assess social support.

Other Self-Report Measures: The following self-report measures will also be collected as part of the TWM trial:

- Demographic and Medical Variables. Common demographic (e.g., gender, age, race/ethnicity, income, educational attainment, employment status) and medical (years since HIV/AIDS diagnosis, time on ART, and medication side-effects) variables will be adapted from prior online studies by this study group.
- Substance Use. Items will be adapted from those used in the TWM pilot study to assess recent (past 5 months) and lifetime illicit drug use and patterns of illicit drug use (i.e., frequency, location, and circumstances of use). The AUDIT (10-item alcohol abuse scale) will be used assess problematic alcohol use.
- Empirically-derived Psychosocial Risk Factors for Poor Adherence. We will assess a broad range of mental health factors with widely-used and validated standardized scales, including the CES-D (10-item depression scale) [14], HIV Symptom Index scale, Perceived Stress Scale (14-items), the Brief Sensation Seeking Scale (BSSS-4) and a 6-item Life Chaos scale, and HIV Stigma scale.
- Technology Use and Internet Knowledge. Participants will indicate how often they access the Internet and for what purposes. Internet knowledge will be assessed with the iKnow measure. Smart phone use will be assessed by asking participants what data plan they have (e.g., unlimited vs. limited vs. no data plan), what mobile phone

carrier they use (e.g., Verizon, AT&T, Sprint), and the frequency of use of smartphone features (e.g., SMS messaging, accessing the Internet on their smartphone).

- Intervention Acceptability. Intervention acceptability items will be drawn from prior research by this research team and from the System Usability Scale. Users will be asked to rate the intervention on system quality, information quality, their overall satisfaction with the application and their beliefs about whether the application improved their health behaviors.
- Finally, user engagement in the TWM intervention will be assessed by: a) frequency of log-ins; b) among log-ins, whether the log-in was via computer, smartphone, or tablet (to assess whether use or outcomes differ by modality by which the intervention is accessed); b) frequency of message posting and responding to other participants' posts; c) frequency of updating medication adherence, drug use, and mood self-monitoring graphs; c) frequency of viewing articles, videos, and links; d) frequency of SMS medication reminders. Among control participants, the number of weekly informational webpages opened and time spent on each weekly webpage will be tracked during the trial period.

The combination of using an experimental design to compare the TWM intervention to control arm participants, and collecting biological, computerized self-report survey data, and user engagement data will allow us to examine the full range of potential effects of the TWM intervention on participant's physical and mental health.

